### 10.1. Primary study endpoint analysis

The main analysis is the comparison of the detection rate of clinically significant cancer (defined as GG $\geq$ 2) between the PCaVision targeted biopsy pathway and the MRI targeted pathway. We will calculate the difference in these detection rates and its corresponding 97.5% confidence interval. Because of the paired design of our study, we will use the approach of Liu which accounts for the correlation between the detection rates of both pathways [44,45,46]. A one-sided 2.5% equivalence test will be performed to formally evaluate whether the lower bound of the confidence interval will not exceed the non-inferiority margin specified at an absolute difference in detection rates of 5%.

As a secondary analysis, the comparison of the proportion of men in whom targeted biopsies could have been safely omitted in the PCaVision pathway compared to the MRI pathway.

This ~~10.2. Secondary study endpoint analysis~~ with respect to detection rate (see above) does not come at the price of fewer patients in whom targeted biopsies can be prevented (e.g., more unnecessary targeted biopsies). For PCaVision this proportion is the number of men in whom there are no lesions to be biopsied based on PCaVision while the MRI biopsy strategy and systematic biopsy (when performed) did not detect clinically significant cancer divided by the total number of men in the study. Likewise, this proportion for MRI is defined as the number of men in whom there are no lesions to be biopsied based on MRI while the PCaVision biopsy strategy and systematic biopsy (when performed) did not

detect clinically significant cancer divided by the total number of men in the study. Given the fully paired nature of the design, the proportions will be tested for being statistically significance different using the McNemar test (two-sided alpha of 5%). The approach of Liu which accounts for the correlation [44,45,46] will be used to calculate a 95% confidence interval for the difference between these proportions.

Furthermore, the same effect measures and statistical approach will be used as in the previous analyses, only the definition of the target condition will change. The following alternative definitions of the target condition (rather than  $ISUP \geq 2$ ) will be used: (i)  $ISUP \geq 3$ ; (ii)  $ISUP \geq 1$ ; (iii)  $ISUP = 1$ . The reason also assessing alternative definitions is that there is still ongoing discussion about the clinical relevance of these histological findings.

Both imaging techniques (PCaVision and MRI) can produce images of insufficient quality impeding the process of taking targeted biopsies. This hampers the clinical usefulness of the imaging technique in practice. Therefore, we will compare the proportion of men in whom the PCaVision pathway produces insufficient-quality images or targeted biopsies with the proportion of men with insufficient-quality MRI images or target biopsies in the MRI pathway. The same statistical approach for paired proportions will be used in the comparison of the detection rate.

The PCaVision software includes automated detection of ultrasound image quality by analysing patient motion and CEUS signal. We will analyse diagnostic accuracy of PCaVision using the same statistical approach with increased requirements of ultrasound images quality with regards to motion and CEUS signal. The exact levels of these increased requirements are described in section 6.1.2.

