### Secondary Objectives

- To compare the proportion of men in whom targeted biopsies could be safely omitted in the PCaVision pathway versus the MRI pathway. This is defined as the number of men in whom no lesions for target biopsies have been identified by PCaVision while no clinically significant cancer is detected in either MRI targeted biopsies or systematic biopsies. The combined findings of all types of biopsies will serve as the reference standard to define 'safe'.
- To perform the same diagnostic accuracy analyses as described in the primary objectives for different definitions of the target condition. This includes: (i)  $ISUP \geq 3$  in any of the biopsy cores taken from a lesion; (ii)  $ISUP \geq 2$  with cribriform growth and/or intraductal carcinoma (CR/IDC) in any of the biopsy cores taken from a lesion; (iii)  $ISUP = 1$ .
- To compare the number of men in whom the PCaVision pathway generated insufficient quality images with the number of men with insufficient quality MRI images in the MRI pathway.
- To perform the same diagnostic accuracy analyses as described in the primary and secondary outcome with different levels of increased criteria for ultrasound image quality, automatically detected by PCaVision

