### 6.1.2 PCaVision quality control

PCaVision is using automated detection of ultrasound image quality by measuring parameters of CEUS and patient motion. Patients will not be processed by PCaVision if they do not fulfil these criteria. Loose criteria are default and used for the primary outcome. A combination of stricter criteria is used for additional (secondary outcome) diagnostic accuracy analysis.

Quality parameter	Specification	Loose	Strict
CEUS signal	Minimum peak intensity value (dB)	43	50
Patient motion	Minimum IoU (intersection over union) of B-mode prostate contours	0.60	0.70
	Maximum root mean square magnitude of detected motion vectors (mm)	8.1	3.0

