## 10. STATISTICAL ANALYSIS

In the analyses, we will compare the histological findings from two main diagnostic pathways: (1) PCaVision imaging in all men followed by targeted biopsies in men with suspicious lesions; (2) MRI imaging in all men followed by targeted biopsies in men with suspicious lesions. The findings will be analysed and reported at the per-patient rather than per-lesion level because the per-patient level of reporting has the greatest clinical relevance. In the analysis, we differentiate between the following two datasets:

- Total study population, all men included in the study to undergo PCaVision and MRI imaging.
- Paired dataset with sufficient quality images and subsequent targeted biopsies for both PCaVision and MRI.

The last dataset will be used in the paired analysis when comparing the diagnostic accuracy of different imaging pathways.

In the descriptive part of the analysis we will show the cross- tabulation of histological findings (ranging from no cancer, GG=1 to GG=5) comparing the two main diagnostic pathways: PCaVision based targeted biopsies against MRI based targeted biopsies.

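### Where systematic biopsy is done only after an MRI lesion, the safe-omission comparison checks PCaVision more strictly than MRI, and no planned analysis shows this; its denominator also needs reconciling

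*Combined protocol and SAP*

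**What the plan says.** **The endpoint.** Sections 2 and 8.1.2 describe safe omission as "the number of men in whom no lesions for target biopsies have been identified by PCaVision while no clinically significant cancer is detected" by MRI-targeted or systematic biopsy. All biopsy types together form the reference, and no denominator is given. The secondary-endpoint text in sections 10.1–10.2 makes it a proportion. For PCaVision the numerator is "the number of men in whom there are no lesions to be biopsied based on PCaVision while the MRI biopsy strategy and systematic biopsy" (where done) found no csPCa, "divided by the total number of men in the study". For MRI: "Likewise, this proportion for MRI is defined as the number of men in whom there are no lesions to be biopsied based on MRI", with PCaVision-targeted and any systematic cores as the check. The two proportions are compared by McNemar at two-sided 5%, with a 95% interval for paired proportions.

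**Systematic biopsy.** The Summary (burden and risks) describes local practice as ranging from all men, through only men with an MRI lesion, to none. It leaves this unchanged because systematic cores do not enter the formal comparison of PCaVision with MRI. Section 5.1 leaves the decision to the local physician.

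**Analysis sets.** Section 10 defines two: "Total study population, all men included in the study to undergo PCaVision and MRI imaging", and "Paired dataset with sufficient quality images and subsequent targeted biopsies for both PCaVision and MRI". It adds: "The last dataset will be used in the paired analysis when comparing the diagnostic accuracy of different imaging pathways". Section 8.4 excludes men with poor imaging or technical problems from analysis. On scans that fail the automated check, section 6.1.2 says: "Patients will not be processed by PCaVision if they do not fulfil these criteria". Section 10.2 gives insufficient quality an endpoint of its own.

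**The concern.** The endpoint is there to show that non-inferior detection is not bought with fewer avoided biopsies. That needs the same standard of safety for both pathways. If an MRI lesion triggers systematic biopsy, the standard depends on the result of one of the two tests being compared. The men who could earn PCaVision an advantage then get an extra search for csPCa, and the men who could earn MRI one do not. The Summary's reason for leaving systematic biopsy to local care fits the primary endpoint, which uses targeted cores only. It does not cover this endpoint, where systematic cores help define safety.

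The smaller issue is the denominator. An all-men denominator sits beside text that sends paired accuracy comparisons to the sufficient-quality set, and the endpoint definition does not say how a man with a failed scan is classified.

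**Working it through.** **Plan's own figures.** The plan gives no expected rate or power for safe omission. Its sample size does reproduce. The paired score formula with 5% + 5% discordant pairs, margin 0.05 and restricted null variance 0.1164 gives n = [1.960·√0.1164 + 0.842·√0.10]² / 0.05² = 349.6, so 350. Then 350 × 1.25 = 437.5, so 438. The allowance is 438 − 350 = 88 men (20.1%).

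**Who drives the test, in a centre where an MRI lesion triggers systematic biopsy**

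| Lesion on | Can count as safe for | Checked by |
|---|---|---|
| MRI only | PCaVision | MRI-targeted + systematic cores |
| PCaVision only | MRI | PCaVision-targeted cores only |
| Neither | both (concordant) | no biopsy |
| Both | neither (concordant) | – |

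Only the first two rows enter McNemar, and they are verified differently. If every man or no man had systematic biopsy, the asymmetry would vanish.

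**Size.** Bias against PCaVision = s × d × y, where all three inputs are assumptions:

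- s, share of men in MRI-triggered centres: 0.2 to 0.8 (1 to 4 of the 5 centres, taken as equal in size).
- d, share of all men in each single-modality-lesion group with no csPCa on the other pathway's targeted cores: 0.10 to 0.20. The 10% discordance in section 4.5 concerns csPCa detection, not lesions, so it cannot supply this.
- y, csPCa found only on systematic cores in such men: 0.05 to 0.10.

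With equal true performance and n = 350, SE of the difference = √(2d × 350)/350. Exact enumeration of McNemar gives the last column; without the bias it is 2.5%.

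| Inputs (s, d, y) | Bias, points | Men of 350 | SE, points | Bias/SE | Wrongly favours MRI |
|---|---|---|---|---|---|
| 0.2, 0.10, 0.05 | 0.10 | 0.35 | 2.39 | 0.04 | 2.8% |
| 0.4, 0.15, 0.075 | 0.45 | 1.6 | 2.93 | 0.15 | 3.6% |
| 0.5, 0.15, 0.075 | 0.56 | 2.0 | 2.93 | 0.19 | 3.9% |
| 0.8, 0.20, 0.10 | 1.60 | 5.6 | 3.38 | 0.47 | 6.9% |

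**Denominator.** If every non-evaluable man is in neither numerator, moving from 350 to 438 multiplies both proportions and their difference by 350/438 = 0.80. As an example, take the Introduction's 259 true negatives per 1,000 men: 0.259 × 350 = 90.65, and 90.65/438 = 20.7% instead of 25.9%. McNemar does not use n. With illustrative discordant counts of 60 and 40, (60 − 40)²/100 = 4.00 and p = 0.046 with either set. The difference is 20/350 = 5.7 points (Tango 95% CI 0.1 to 11.3) or 20/438 = 4.6 points (0.1 to 9.1).

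**The case against.** **On verification.** The documents do not say that any of the five centres uses the MRI-triggered policy. Section 5.1 would also let a physician take systematic cores in an MRI-negative man who is already being biopsied for a PCaVision lesion. The endpoint is secondary, the bias runs against the investigational device, and at mid-range inputs it is about 0.5 point, under 0.2 SE. The 6.9% needs every input at its assumed maximum. All of this stands and limits the weight of the point. It does not remove the mechanism, which follows from the endpoint definition together with a local policy that the Summary itself describes, and no planned analysis would reveal it.

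**On the denominator.** Sections 8.4 and 10 already point to leaving out insufficient scans, so the plan is not silent. What is left is a conflict of wording. The choice between complete cases and all men is also open to fair dispute.

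**Stronger readings the documents do not support.**

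- A reader might infer that the primary non-inferiority result is compromised. It uses targeted biopsies only, so unequal verification does not reach it.
- A reader might infer that the all-men denominator changes the test or always shrinks results by 0.80. McNemar is unchanged in that case. The factor is an extreme: a man whose PCaVision scan alone fails could still count for MRI, and section 4.5 also expects some losses from technical problems at biopsy.
- A reader might infer from section 6.1.2 that failed scans will be credited to PCaVision as lesion-free, and that the difference could move by about 7 points. That figure needs all 88 men to be PCaVision-only failures and an assumed 35% safe-omission rate. Counted as not omitted, the shift is −0.35 × 88/438 = −7.0 points. Counted as lesion-free with an assumed 70% clean elsewhere, it is (0.70 − 0.35) × 88/438 = +7.0 points. The documents give no split of failures by modality, and section 8.4 points to exclusion.

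**Conclusion.** The verification point holds, conditionally. In any centre where systematic biopsy follows only an MRI lesion, the two groups that decide McNemar are checked unequally, and the comparison is biased against PCaVision to the extent that systematic cores alone find csPCa. The size cannot be known from the documents. Under the assumed ranges it is 0.1 to 1.6 points, and it is zero if no centre works this way. A significant result in MRI's favour would be harder to trust; one in PCaVision's favour would not be explained by this bias.

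The denominator is a minor point: two parts of the plan need reconciling. The test result can change only if failed scans are classified differently by pathway, and one sentence can rule that out. Overall this is a cheap improvement to a secondary endpoint.

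**What to change.** **Verification.**

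- Keep the combined-biopsy definition of safe omission as the main analysis.
- Add a sensitivity analysis that defines safety by the other pathway's targeted biopsies only, so both discordant groups are verified alike.
- Tabulate how many men in each discordant group had systematic biopsy.

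**Analysis set.**

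- In the secondary-endpoint text of section 10, name one set for numerator and denominator, and reconcile it with section 8.4 and the dataset definitions.
- State that an unprocessed or insufficient scan is never counted as showing no lesion.
- Report the other analysis set as a sensitivity analysis.
- If the paired set is chosen, define it with targeted biopsies taken where indicated, as section 4.5 does for the 350. Read literally, a requirement for targeted biopsies from both techniques would drop the lesion-free men whom this endpoint counts.

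**Cost.** A few sentences, two sensitivity analyses and one descriptive table. No new patients or procedures are needed: biopsy pathology reports are already study data (section 12.1.2), and section 8.2 has systematic cores read where available. The targeted-only definition misses cancers found only on systematic biopsy, so it should stay a sensitivity analysis. Choosing the paired set as the main one lowers the denominator to about 350 from 438.

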**Nature and extent of the burden and risks associated with participation, benefit and group relatedness:**

In most participants centres, local clinical care would consist of MRI-target and (potentially) systematic biopsies. Local clinical care can differ between hospitals with respect to systematic biopsies; varying from standard in all, only in men with one or more lesions on MRI, to no systematic biopsies at all. This part of usual care will not change in the current study. Systematic biopsies play no role in the formal head-to-head comparison between PCaVision and MRI. Evaluating whether PCaVision is non-inferior to MRI requires only the comparison of the findings from the targeted biopsies of both strategies. Consequently, there is no change in the quality of current care.

There could be a potential benefit for the participants in this study when PCaVision detects additional cancers missed by MRI. Furthermore, the study results may be important for future patients suspected for prostate cancer. If PCaVision is sufficiently accurate, it could coexist with MRI as the central imaging strategies which would lead to a more streamlined and more cost-effective diagnostic work-up, especially in centres with moderate MRI quality, or centres lacking MRI capacity.

In this study, additional targeted biopsies could be performed because of the identification of PCa on PCaVision imaging. These extra biopsies also carry a small risk of haemorrhage and infection. There is also a small, anticipated risk for participants associated with the administration of ultrasound contrast. However, adverse events caused by the ultrasound contrast agent appear to be transient, mild, and rare.

In conclusion, although the potential benefit for the patient is small, we also believe that the burden and risk associated with participation in this study is limited.

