0.83-0.95) and a specificity of 0.37 (95% CI: 0.29-0.46) [9]. Per one-thousand men, with an expected prevalence of 30% of clinically relevant cancer, MRI scanning may result in 273 true positives, 259 true negatives, but may still lead to 441 false positives (unnecessary biopsies and potential for overtreatment) and 27 false negatives (missed relevant cancers by MRI) [9]. These results are from high quality, high volume centers, however, apart from these results, there was a large variation in the sensitivities and specificities for MRI between individual studies [10,11] which can be attributed to a difference in MRI equipment, study design and inter-observer variability [12,13,14]. Next to its limited availability, MRI is a time-consuming, expensive imaging modality which is not available at bedside and requires highly trained radiologists for interpretation. Moreover, the added value of the dynamic contrast-enhanced MRI (DCE-MRI) sequence in comparison with MRI without contrast enhancement in different risk scenarios in biopsy-naïve men is being discussed.

However, greater evidence is needed to precisely define which patient groups benefit from contrast enhancement and who can safely avoid it [15].

Ultrasound (US), is widely available, cheaper to implement and familiar to the urologist, however, it is currently recommended for prostate biopsy guidance only [8]. New US

modalities including contrast-enhanced US (CEUS), micro-US and (shear wave) elastography have been introduced to improve US-based diagnosis of PCa [16,17,18].

In CEUS, an ultrasound contrast agent is injected intravenously to enhance imaging [19]. The dispersion of the ultrasound contrast agent in the vascular network is measured over time, enabling visualization of angiogenesis. PCa requires angiogenesis to be able to progress into clinically significant disease [20]. Moreover, the degree of angiogenesis has been shown to correlate to the aggressiveness of PCa [21-23].

In a previous study, CEUS quantification predicted 72.2% of biopsy locations as benign, resulting in a false negative rate of 2.6%. Thirty-one of eighty-two patients were classified as not having a malignant focus, resulting in a missed diagnosis in three patients. The sensitivity and specificity of CEUS were 91% and 56%, respectively [24].

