## 5. TREATMENT OF SUBJECTS

### 5.1. Investigational treatment

In this study, all men will undergo both MRI and PCaVision imaging. Two different specialists will perform these imaging who are unaware of the results of the other imaging technique.

MRI images will be read by an experienced uro-radiologist and suspicious lesions will be marked. An experienced urologist will read the PCaVision images and mark suspicious lesions. This will ensure that suspicious lesions will be identified based on each imaging technique independently (i.e., blinded for the other imaging technique).

A MRI targeted 3-core biopsy per lesion (with a maximum of 2 lesions) and/or a PCaVision targeted 3-core biopsy per lesion (with a maximum of 2 lesions) will be performed by a urologist if suspicious lesions have been identified based on imaging. The maximum number of targeted biopsies per imaging technique is 6. Each biopsy sample will be collected in a separate container. As a result, there will be maximally 6 containers with samples from the PCaVision targeted biopsy, and 6 containers with samples from the MRI targeted biopsy.

If no suspicious lesions have been identified by an imaging technique, no targeted biopsies based on that imaging technique will be performed. It is up to the local physician whether routine systematic biopsies will be taken.. If suspicious lesions have been identified with both PCaVision and MRI in the same patient, the order of the targeted biopsies will be randomized. Randomization of the order will prevent any systematic advantage of performing the targeted biopsies of one imaging technique always before the other technique.

Moreover, if the clinician suspects that the same lesion has been identified by both PCaVision and MRI, both PCaVision and MRI targeted biopsies of this lesion will be performed. This event will be documented. The outcome of the evaluation of the collected samples obtained by both PCaVision and MRI targeted biopsies will be compared to ensure that there is no deviation in outcome resulting from the order of targeting the same lesion. It is up to the local physician whether routine systematic biopsies will be taken beside these target biopsies. All biopsies will be performed in a single visit.

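### Men negative on both techniques and without systematic biopsy count as safely omitted with no histology, so each pathway's absolute 'safe' proportion is an upper bound

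*Combined protocol and SAP*

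**What the plan says.** Section 10.2 (its heading falls inside the text of 10.1) defines the numerator for PCaVision as men with "no lesions to be biopsied based on PCaVision while the MRI biopsy strategy and systematic biopsy (when performed) did not detect clinically significant cancer". The MRI numerator mirrors it: "no lesions to be biopsied based on MRI while the PCaVision biopsy strategy and systematic biopsy (when performed) did not" find such cancer. Both are "divided by the total number of men in the study". The two proportions are compared with a two-sided 5% McNemar test and a Liu-type 95% confidence interval for the paired difference.

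Three other places decide who has histology:

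- Section 2, secondary objectives (repeated in 8.1.2): "The combined findings of all types of biopsies will serve as the reference standard to define 'safe".
- Section 5.1: "If no suspicious lesions have been identified by an imaging technique, no targeted biopsies based on that imaging technique will be performed". Systematic biopsy is left to the local physician, and Section 8.2 allows for men with no targeted procedure at all.
- Summary, burden and risks: local practice for systematic biopsy is described as "varying from standard in all, only in men with one or more lesions on MRI, to no systematic biopsies at all".

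The plan has no rule for a man without any biopsy. It does not exclude him, count him separately, impute his status or bound the result. Follow-up in 5.3 covers biopsy complications only, and 12.1.3 says that men are not contacted again after the study.

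**The concern.** For a man with no lesion on either technique and no systematic biopsy, the condition that no significant cancer was detected is met automatically. No outcome enters the rule, and he is counted as safe in both pathways whether or not he has cancer. This conflicts with a reference standard built on biopsy findings.

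The reported proportions therefore mix men shown to have no significant cancer on the biopsies taken with men who were never checked, and the mix depends on local policy. A reader who takes the absolute figure as the share of men who can safely go without targeted biopsy cannot tell how much of it rests on histology.

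**Working it through.** **Plan's own figures.** The plan states no expected safe-omission proportion, so there is none to reproduce. The MRI figures in Section 1 per 1,000 men, used below, do reproduce: 1,000 × 0.30 × 0.91 = 273 true positives, 300 − 273 = 27 missed, 1,000 × 0.70 × 0.37 = 259 true negatives, 700 − 259 = 441 false positives.

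**Inputs**

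- Prevalence 30%, MRI sensitivity 0.91 and specificity 0.37: Section 1.
- PCaVision: sensitivity 0.83 and specificity 0.55, reported in Section 1 for 2D CUDI. This is a weak stand-in. It is an older 2D method, and the title of the cited study refers to radical prostatectomy specimens, so its specificity may not carry over to biopsy-naïve men.
- 350 evaluable men: Section 4.5.
- Not in the documents, so ranged: *c*, the share of both-negative men who get systematic biopsy (0 to 1), and the overlap of the two techniques' negative results (independent given disease, to maximal).
- Assumption: biopsies find the significant cancer that they check for.

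**Formula.** Let D1 be the share of men negative on both techniques with significant cancer, and D0 the share negative on both without it.

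- True safe proportion = P(index technique negative, no cancer): PCaVision 0.70 × 0.55 = 38.5%; MRI 0.70 × 0.37 = 25.9%.
- Proportion under the rule = true proportion + (1 − c) × D1.
- Proportion counting only men with histology = true proportion − (1 − c) × D0.

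The second line cannot fall as *c* falls, so the rule gives an upper bound. It is exact only if c = 1 or D1 = 0.

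| | Independent errors | Maximal overlap |
|---|---|---|
| D1 | 0.30 × 0.09 × 0.17 = 0.0046 | 0.30 × 0.09 = 0.0270 |
| D0 | 0.70 × 0.37 × 0.55 = 0.1425 | 0.70 × 0.37 = 0.2590 |
| Negative on both (D1 + D0) | 14.7% | 28.6% |
| Of 350, no histology at c = 0 | about 51 | about 100 |
| PCaVision under the rule, c = 1 / 0.5 / 0 | 38.5 / 38.7 / 39.0% | 38.5 / 39.9 / 41.2% |
| MRI under the rule, c = 1 / 0.5 / 0 | 25.9 / 26.1 / 26.4% | 25.9 / 27.3 / 28.6% |
| Difference, every c | 12.6 points | 12.6 points |
| Histology only, c = 0: PCaVision / MRI | 24.3 / 11.7% | 12.6 / 0% |

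At c = 0 the overstatement is D1, that is 0.5 to 2.7 points in each pathway. With the other contrast-ultrasound figures in Section 1 (0.91 and 0.56) as stand-in, D1 runs from 0.30 × 0.09 × 0.09 = 0.0024 to 0.0270, so 0.2 to 2.7 points.

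**Is a positive D1 plausible?** Section 1 implies 27/(259 + 27) = 9.4% significant cancer among MRI-negative men, and reports 3 missed diagnoses in 31 CEUS-negative men (9.7%). The rate in men negative on both is not given, but these figures make zero unlikely.

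**Paired comparison.** A both-negative man is in both numerators or, if he were reclassified, in neither. Either way he is a concordant pair. The discordant counts and the number of men do not change, so the difference, its interval and McNemar's test do not change.

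**The case against.** The strongest reply is that the objective is a comparison. The surviving text of 10.2 presents the endpoint as a check that the detection result is not bought with fewer avoided biopsies, which is a contrast, and both-negative men cancel from it. This stands. Only the two absolute proportions are affected, and neither is tested on its own.

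The bias is also small on these inputs: 39.0% against 38.5% for PCaVision and 26.4% against 25.9% for MRI with independent errors. A reader might take the unverified share of each figure (0.147/0.390 = 38% for PCaVision, 0.147/0.264 = 56% for MRI) as the size of the error. It is not: most of these men would have no significant cancer.

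A reader might conclude that only men with histology should count as safe. In the independent case that gives 24.3% and 11.7% against true values of 38.5% and 25.9%, about 14 points too low, and so much further from the truth than the current rule.

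A reader might also link this endpoint to the statements in Sections 11.3 and 13 that systematic biopsy could one day be dropped after a negative ultrasound. Those statements rest on PCaVision being sensitive enough and concern systematic biopsy. This endpoint concerns targeted biopsy, so the documents do not make that link.

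What the reply leaves unanswered is that the plan defines and will report a proportion labelled safe, names biopsy findings as its standard, and has no provision for men who have none.

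**Conclusion.** The point holds for the absolute proportions. As defined, each pathway's figure is an upper bound that partly reflects local systematic biopsy policy. If no both-negative man has systematic biopsy, about 15% to 29% of men would be called safe without histology, and each proportion would be overstated by about 0.5 to 2.7 points. If all of them have it, the overstatement is zero. These sizes rest on a weak stand-in for PCaVision, and on coverage and overlap that the documents do not give.

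A reader might infer that the comparison between pathways is biased by these men. It is not, because they are concordant. The primary non-inferiority analysis does not use this rule.

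**What to change.** In Section 10.2, keep the rule and the McNemar and Liu analyses, and add three things:

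1. For each pathway, report the number of omitted men with histology (the other technique's targeted cores or systematic cores) and the number with none.
2. Give the absolute safe proportion with two bounds: men without histology all counted as unsafe, and all counted as safe. Label the figure from the current rule as the upper bound.
3. State that the histology-only figure is a lower bound and not an estimate. Do not redefine safe in that way.

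An estimate that applies the cancer rate of both-negative men who had systematic biopsy, from centres that take it in all men, is optional and exploratory. If one of five equal centres did so, the expected number of events would be only 350 × 0.0046/5 = 0.3 to 350 × 0.027/5 = 1.9.

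The cost is a few lines of text and one extra table from data already collected, with no added biopsies or patients. The downside is a wider stated range for a secondary endpoint: in the independent case at c = 0, 24.3% to 39.0% for PCaVision and 11.7% to 26.4% for MRI.
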